8. CRITERIA FOR EVALUATION AND ENDPOINT DEFINITION

8.1 Primary Endpoint

- 8.1.1 To determine the effect of PROSTVAC® on the change (pre to post-intervention) in CD8⁺ positive cells in the stroma adjacent to tumor and within the malignant portion of the prostate biopsies. The change will be compared between participants treated with PROSTVAC® and those treated with placebo. A subgroup analysis will be performed to compare the change in CD8⁺ positive cells between study groups in specimens collected by targeted biopsy.
- 8.1.2 To determine the effect of PROSTVAC® on the change in CD4⁺ positive cells in the stroma adjacent to tumor and within the malignant portion of the prostate biopsies. The change will be compared between participants treated with PROSTVAC® and those treated with placebo. A subgroup analysis will be performed to compare the change in CD4⁺ positive cells between study groups in specimens collected by targeted biopsy.

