13.4 Primary Objective, Endpoint(s), Analysis Plan

The primary objectives of this study are to determine the effects of PROSTVAC® on the change (from pre- to post-intervention) in CD8⁺ and CD4⁺ positive cells in the stroma adjacent to tumor and within the malignant portion of the prostate biopsies.

The primary endpoints are the change in CD8⁺ and CD4⁺ positive cells in the stroma adjacent to tumor and within the malignant portion of the prostate biopsies. The change in CD8⁺ and CD4⁺ positive cells will be compared between participants treated with PROSTVAC® and those treated with placebo. We project an attrition rate of 10% (with respect to completing the intervention and providing post intervention biopsy) and 70% of the post intervention biopsy would have tumor. We plan to randomize 150 eligible participants to receive PROSTVAC® or placebo at a 2:1 ratio to have 63 and 31 subjects in the PROSTVAC® group and the placebo group, respectively, with primary endpoint data. A two-sided two-sample t test will be used to compare the change in CD4⁺ and CD8⁺ positive cells in tumor tissue between the treatment and placebo groups. Based on a sample size of 63 in the PROSTVAC® group and 31 in the placebo group and assuming that the standard deviation of the change in CD8⁺ and CD4⁺ positive cells for the PROSTVAC group is twice that of the placebo group, the power will be at least 90% to detect a Cohen's d effect size (i.e. the difference between the two groups divided by the pooled standard deviation) of ≥ 0.63 at a significance level of 5% by the Bonferroni correction (i.e., a significance level of 2.5% for each). MI techniques will be performed, as needed, for the participants without endpoint data. If MI is deemed necessary, the variables that are predictive of missing endpoint data will be incorporated into MI. The "available" sample size after MI is expected to be larger than the estimated sample size. Hence, we are confident of detecting effect sizes smaller than the above effect sizes after applying the Rubin's rules since the predictive variables used in MI can improve efficiency and reduce potential bias due to missing data.

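### Testing CD8 and CD4 by Holm instead of single-step Bonferroni would raise power for both markers from about 82–84% to 89–90% at the same 5% family-wise error

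*Combined protocol and SAP*

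**What the plan says.** Section 13.4 of the combined protocol and SAP names two primary endpoints, the change in CD8 and the change in CD4 cells. For each marker, "A two-sided two-sample t test will be used to compare the change" between arms. The overall level is split equally and in one step: "at a significance level of 5% by the Bonferroni correction (i.e., a significance level of 2.5% for each".

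The power statement is made per marker. "Based on a sample size of 63 in the PROSTVAC® group and 31 in the placebo group", and with the assumption that the SD of the change "for the PROSTVAC group is twice that of the placebo group", "the power will be at least 90% to detect" a Cohen's d, defined as "the difference between the two groups divided by the pooled standard deviation) of ≥ 0.63".

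On tissue, section 8.1 (like 1.1) refers each marker to "positive cells in the stroma adjacent to tumor and within the malignant portion of the prostate biopsies". The test sentence in 13.4 uses a shorter description: "positive cells in tumor tissue between the treatment and placebo groups". Neither section says how the two regions are combined into one value.

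**The concern.** With two co-primary markers, single-step Bonferroni holds the second marker to 2.5% even when the first has already been shown at 2.5%. That strictness is not needed to keep family-wise error at 5%. Once one null hypothesis has been rejected, only one can still be true, and it can be tested at the full 5%. Holm's procedure does this. It rejects everything that Bonferroni rejects and sometimes more.

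At stake is the conclusion on the second marker. A trial with CD8 at p = 0.01 and CD4 at p = 0.04 would claim only CD8 under the current plan, but both under Holm with the same error guarantee. Because the objectives ask about each marker in its own right, this loss matters.

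**Working it through.** **Inputs (section 13.4).** n = 63 and 31; SD ratio 2:1; d = 0.63 on the pooled SD; two-sided 2.5% per marker; stated power at least 90%. The correlation between the two test statistics is not in the documents, so I assume 0, 0.5 and 0.8.

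**Step 1: the plan's error rate.** Two tests at 2.5% give at most 2 × 0.025 = 5.0%, or 1 − 0.975² = 4.94% if independent. The 5% claim is correct.

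**Step 2: the plan's power.** Set the placebo SD to 1 and the PROSTVAC SD to 2.
- Pooled SD, weighted by degrees of freedom: √[(62 × 4 + 30 × 1)/92] = √3.022 = 1.738
- Difference: 0.63 × 1.738 = 1.095
- Unequal-variance standard error: √(4/63 + 1/31) = √0.09575 = 0.3094
- Standardised effect: 1.095/0.3094 = 3.539
- Power at two-sided 2.5%: Φ(3.539 − 2.241) = Φ(1.298) = 90.3%

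The noncentral t version gives 89.4%. The plan's 90% is therefore reproduced, but only with an unequal-variance (Welch) test and this pooled SD. A Student t test under the same 2:1 SDs gives 76.7% by simulation.

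**Step 3: Holm, independent markers.** Power at two-sided 5% is Φ(3.539 − 1.960) = Φ(1.579) = 94.3%. Write A = 0.9028 (power at 2.5%) and B = 0.9429 (power at 5%).
- Both markers, Bonferroni: A² = 81.5%
- Both markers, Holm: B² − (B − A)² = 0.8890 − 0.0016 = 88.7%. The subtracted term is the case where both p-values lie between 2.5% and 5%, so the first step fails.
- Per marker, Holm: A + (B − A) × A = 0.9028 + 0.0401 × 0.9028 = 93.9%, against 90.3%
- At least one marker, either method: 1 − (1 − A)² = 99.1%

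**Step 4: Holm, correlated markers.** The same events, evaluated with the bivariate normal distribution:

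| Assumed correlation | Both: Bonferroni | Both: Holm | Per marker: Bonferroni | Per marker: Holm | At least one (either) |
|---|---|---|---|---|---|
| 0 | 81.5% | 88.7% | 90.3% | 93.9% | 99.1% |
| 0.5 | 83.7% | 89.7% | 90.3% | 93.3% | 96.9% |
| 0.8 | 86.0% | 90.8% | 90.3% | 92.7% | 94.6% |

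**Step 5: Holm's error rate.** If both nulls are true, a false rejection needs the smaller p-value to be below 2.5%, exactly as under Bonferroni. If one null is true, it is tested at 5% at most. Family-wise error is therefore at most 5% whatever the correlation. Simulation of the two-test case agrees: at most 4.96% under the global null, and at most 4.8% with one true effect.

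**Step 6: the tissue wording.** Section 13.4 gives one comparison per marker and divides the level by two. Sections 1.1 and 8.1 each list exactly two primary items. Section 8.2.2 treats the CD8 change over stroma and malignant portion as a single variable to correlate with PSA. Where a separate tissue analysis is wanted (the benign portion, 8.2.3), it has its own endpoint. Together these describe two primary tests.

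**The case against.** Bonferroni is prespecified, valid and conservative, and the plan's power claim is for each marker at 2.5%, which it meets. No success criterion requires both markers, and Holm does not change the chance of at least one positive. All of that stands, so the current choice is not an error. It does not count against Holm, which loses nothing in error control or power and gains where the second marker is concerned. Holm's simultaneous confidence intervals are less simple, which is a genuine drawback, but a small one here because 13.4 plans no multiplicity-adjusted intervals for the primary comparison.

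A reader might go further and infer that, because two tissue regions are named for each marker, the plan runs four tests at 2.5% and so has a family-wise error near 10%. The documents do not support this. No section specifies four primary tests, and the passages in step 6 point to one value per marker. Only if the regions were tested separately at 2.5% each would the error exceed 5%: 1 − 0.975⁴ = 9.6% if independent, at most 4 × 2.5% = 10.0%, and lower with positive correlation (8.5% with all pairs at an assumed 0.5). What remains is a missing detail, namely how the regions are combined. Holm does not supply it, since the number of tests must be fixed first.

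**Conclusion.** The planned correction is valid, but a uniformly better one is available. For the same two tests and the same 5% family-wise error, Holm adds about 6 to 7 percentage points of power for both markers (81.5% to 88.7% if independent; 83.7% to 89.7% at correlation 0.5) and about 3 to 4 points per marker. It adds nothing to the chance of at least one positive.

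The gains rest on both markers having the planned d = 0.63, on 63 v 31 evaluable participants with a 2:1 SD ratio, on an unequal-variance test, on a normal approximation and on an assumed correlation. At 0.8 the gain for both markers is about 5 points. That Holm is never worse rests on none of these assumptions.

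This is an optional improvement to a sound plan. The tissue wording needs clarifying but is not evidence of inflated error.

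**What to change.** In 13.4, replace the fixed 2.5% per marker with Holm at a two-sided family-wise 5%: test the smaller of the CD8 and CD4 p-values at 2.5%; if it is significant, test the other at 5%; otherwise stop. The rule works on p-values, so it carries over unchanged to the planned transformations, rank tests or multiply imputed analyses. The existing sample size and per-marker power statement can stay, since 90% at 2.5% becomes a lower bound. Name the t test as the unequal-variance version, because that is what the stated power assumes.

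As a clarification, state in 8.1 and 13.4 that each marker has one primary value covering malignant tissue plus adjacent stroma, say how the two are combined, and list region-specific results as secondary. The unit and weighting are for the study team to choose, as the documents give neither.

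The cost is a few sentences of wording, with no added participants or assays. Since 13.9 says the primary endpoints are analysed in batches at the end of the study, the change should be made before those data are available.

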13.5 Secondary Objectives, Endpoints, Analysis Plans

The secondary objectives are to determine the effects of PROSTVAC® on the change in PD-L1 positive cells in the stroma adjacent to tumor and within the malignant portion of the prostate biopsies, the correlation between the change in CD8⁺ and the change in PSA, to determine the effect of PROSTVAC® on the change in CD8⁺, CD4⁺, and PD-L1 positive cells in the benign portion of the prostate biopsies, to determine the effect of PROSTVAC® on the change in PSA, to assess the effect of PROSTVAC® on tumor grade and tumor extent, to assess the proportion of men with no cancer on the post-intervention biopsy, to assess the safety and feasibility of PROSTVAC®, and to assess the effects of PROSTVAC® on LUTS.

The secondary endpoints include the change in PD-L1 positive cells in the stroma adjacent to tumor and within the malignant portion of the prostate biopsies, the correlation between the change in CD8⁺ and the

change in PSA, the change in CD8⁺, CD4⁺, and PD-L1 positive cells in the benign portion of the prostate biopsies, the change in PSA, the tumor grade progression, the change in tumor extent, safety and feasibility, and the change in International Prostate Symptom Score. In addition, a comparison will be made between the two study arms on the proportion of patients with no cancer on the post-intervention biopsy. Similarly, MI techniques will be performed, as necessary. A two-sided two-sample t test at a significance level of 5% will be performed to compare each of the secondary endpoints between the PROSTVAC® and placebo groups. Pearson correlation coefficient will be derived to evaluate the correlation between the change in CD8⁺ and the change in PSA for participants treated with PROSTVAC®. Fisher's exact test will be performed to compare the proportion of patients with no cancer on the post-intervention biopsy and the proportion of men with an increase in Gleason score to $\geq 4+3$ between the two groups. These secondary analyses are considered exploratory, therefore, no correction will be performed for multiple comparisons.

For both primary and secondary endpoints, data will be tested for non-normality and outliers. If the normality assumption is violated, a potential transformation will be sought. If no suitable transformations can be found, nonparametric tests (e.g. Wilcoxon Rank Sum test and Spearman correlation coefficient) will be used. If outliers are detected, sensitivity analysis will be performed to evaluate the impact of the outliers on the effects of PROSTVAC®. In addition, we anticipate observing a missing rate of 25% or greater for both primary and secondary endpoints. The missing rates for both PROSTVAC® and placebo groups will be reported and compared. Also, regression models will be performed to identify the potential variables that are predictive of the missing endpoints or probabilities.

Descriptive statistics of the type and frequency of all adverse events will be generated, including 95% confidence intervals. For each type of the adverse events, a Fisher's exact test will be performed to compare the frequency of the adverse event between the two groups.

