4. PARTICIPANT SELECTION

4.1 Inclusion Criteria

- 4.1.1 Biopsy-proven (consisting of ≥ 10 tissue cores) adenocarcinoma of the prostate with cancer present in at least one biopsy core, either random or targeted, in the most recent biopsy.
- 4.1.2 All prior biopsies must meet the following: $\leq 50\%$ of the total number of random biopsy cores positive for cancer
 - Gleason score $\leq (3+4)$
- 4.1.3 Clinical stage $\leq T2a$ by DRE
- 4.1.4 Biopsies performed at outside institutions should have Gleason score confirmed at the study site by a GU pathologist to ensure eligibility.
- 4.1.5 Pre-intervention biopsy tissue (most proximal to enrollment) containing sufficient tumor tissue to cut 5-10 unstained slides confirmed to be available upon request.
- 4.1.6 Screening serum PSA < 20 ng/mL. For men treated with 5-alpha-reductase inhibitors (e.g., finasteride, dutasteride), PSA needs to be < 10 ng/mL.
- 4.1.7 Hematological eligibility parameters:
Neutrophil count $\geq 1,200/\text{mm}^3$ (≥ 1.2 k/ μL)
Stable platelet count $\geq 75,000/\text{mm}^3$ (≥ 75 k/ μL)
- 4.1.8 Hepatic and renal function eligibility parameters:
Bilirubin ≤ 1.5 mg/dL (or ≤ 3.0 mg/dL for patients with Gilbert's syndrome)
ALT and AST ≤ 2.5 x ULN
Serum creatinine ≤ 1.5 x ULN
- 4.1.9 Karnofsky $\geq 70\%$; see Appendix A.
- 4.1.10 Must agree to use medically acceptable barrier and/or chemical method of contraception while on study and for at least one month following the last vaccine injection because the effects of PROSTVAC® on the developing human fetus at the recommended therapeutic dose are unknown. Should a participant's partner become pregnant or suspect she is pregnant while the participant is participating in this study, the study physician should be informed immediately. In the event a participant's partner becomes pregnant, the study sponsor may request additional information regarding the course of the pregnancy and if the pregnancy is carried to term, the birth of the child (i.e., the outcome of the pregnancy).
- 4.1.11 Ability to understand and the willingness to sign a written informed consent document.
- 4.1.12 No planned prostate biopsies during the intervention until after the post-intervention biopsy.
- 4.1.13 Men on stable doses of 5-alpha reductase inhibitors are eligible as long as there is no planned dose change while on study.

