8.2 Secondary Endpoints

- 8.2.1 To assess the effect of PROSTVAC® on the change in PD-L1 positive cells in the stroma adjacent to tumor and within the malignant portion of the prostate biopsies. The change will be compared between participants treated with PROSTVAC® and those treated with placebo. A subgroup analysis will be performed to compare the change in PD-L1 positive cells between study groups in specimens collected by targeted biopsy.
- 8.2.2 To assess the correlation between the change in CD8⁺ and the change in PSA. The correlation between the change in CD8⁺ in the stroma adjacent to tumor and within the malignant portion of the prostate biopsies and the change in PSA (from baseline to 6 months (5-7 months) post-intervention) in participants treated with PROSTVAC® will be examined.
- 8.2.3 To assess the effect of PROSTVAC® on the change in CD8⁺, CD4⁺, and PD-L1 positive cells in the benign portion of the prostate biopsies. The change will be compared between participants treated with PROSTVAC® and those treated with placebo.
- 8.2.4 To assess the effect of PROSTVAC® on the change in PSA. The change in PSA from baseline to 6 months (5-7 months) post-intervention will be compared between participants treated with PROSTVAC® and those treated with placebo.
- 8.2.5 To assess the effect of PROSTVAC® on tumor grade progression, defined as a post-intervention

- Gleason score of $\geq 4+3$ using all biopsy data, i.e., from random and target biopsy cores. Proportion of men with post-intervention Gleason score of $\geq 4+3$ will be compared between the treatment groups. In addition, this endpoint will be evaluated in the subgroup of patients in whom MRI-targeted biopsies were obtained pre- and post-intervention.
- 8.2.6 To assess the effect of PROSTVAC on tumor extent based on the percent of positive random biopsy cores. The change in tumor extent will be compared between the treatment groups.
 - 8.2.7 To assess the proportion of men with no cancer in the post-intervention biopsy between participants treated with PROSTVAC® and those treated with placebo. This analysis will utilize all biopsy data, i.e., from random and target biopsy cores.
 - 8.2.8 To assess the effect of PROSTVAC on the size of the dominant lesion on MRI (largest histopathologically confirmed lesion) in the subgroup of patients with MRIs pre and post-intervention.

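### Optional, near-costless gain: adjust the no-cancer-on-repeat-biopsy comparison (8.2.7) for baseline positive-core count, which the valid Fisher test in 13.5 leaves unused

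*Combined protocol and SAP*

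**What the plan says.** - **Entry.** Section 4.1.1 requires biopsy-proven adenocarcinoma "with cancer present in at least one biopsy core, either random or targeted, in the most recent biopsy". Section 4.1.2 sets a ceiling of half "of the total number of random biopsy cores positive for cancer". Baseline burden can therefore run from a single core to half of the random cores.
- **Endpoint.** Section 8.2.7 compares between arms the "proportion of men with no cancer in the post-intervention biopsy" and adds: "This analysis will utilize all biopsy data, i.e., from random and target biopsy cores". No minimum change and no confirmatory biopsy is required.
- **Expected rate.** The only relevant figure is in section 13.4, where it is used to size the primary endpoints: "70% of the post intervention biopsy would have tumor". No reason is given for the other 30%, and no rate specific to placebo.
- **Test.** Section 13.5 states that a Fisher's "exact test will be performed to compare the proportion of patients with no cancer on the post-intervention biopsy", and names no covariate or stratum. It calls the secondary analyses exploratory and applies no multiplicity correction.
- **Randomization.** Section 13.2 stratifies by site and number of repeat biopsies, not by core count.
- **Available data.** Sections 3 and 7.4 provide for collecting the pre- and post-intervention pathology reports. Endpoint 8.2.6 already uses the percentage of positive random cores.

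**The concern.** A man qualifies with one positive core and counts as "no cancer" with none on a single later biopsy. A man who entered on one small focus can cross that line more easily than a man who entered with half of his random cores positive. If so, baseline core count is a strong prognostic factor for this endpoint. It is fixed before randomization and already on file, yet the planned test ignores it.

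Two things are at stake. One is power, in a comparison with only about 45 biopsied men on placebo. The other is interpretation: if about three in ten biopsies in each arm are expected to be negative, the proportion in the vaccine arm taken alone says little about the vaccine.

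**Working it through.** **1. The plan's own figure.** Section 13.4 assumes 10% attrition and 70% with tumor: 100 × 0.90 × 0.70 = 63 and 50 × 0.90 × 0.70 = 31.5 (given as 31). Both reproduce, which shows that the plan applies the 30% tumor-negative rate to placebo as well as to vaccine.

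**2. Men available for 8.2.7.** 100 × 0.90 = 90 and 50 × 0.90 = 45. At 30% negative in each arm that is 27 and 13.5 men. Multiple imputation is left out of what follows.

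**3. The planned test.** Exact enumeration of two-sided Fisher at 90 v 45 gives a size of 3.9% at 30% v 30%, so there is no false-positive inflation. From a 30% placebo rate, power is 17% for a difference of 10 points, 36% for 15, 58% for 20, 78% for 25 and 91% for 30.

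**4. Why core count could matter.** The documents give no figure, so this step is assumption. If each of 12 cores is independently positive with probability q, the chance of a negative biopsy is (1 − q)^12: 35% at q = 1/12, 11% at 2/12 and 3% at 3/12.

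**5. Model for the gain (assumed).** Each man has a core-positivity probability drawn from Beta(a, b). He enters if k of 12 cores are positive, with k from 1 to 6 (6 being half of 12). His chance of a negative 12-core repeat biopsy is B(a + k, b + 24 − k) / B(a + k, b + 12 − k), where B is the beta function. For each a, b is chosen so that the average is 30%. The vaccine multiplies the odds of a negative biopsy by 2.5 at every k. The stratified statistic, with strata k = 1, 2 and 3 or more, is

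[Σ(x − n1·m/n)]² / Σ[n1·n0·m·(n − m) / (n²(n − 1))], referred to chi-square on 1 df.

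In each stratum, x is the number of negative biopsies on vaccine, m the total number negative, n1 and n0 the arm sizes, and n their sum. Small a means that men differ greatly; large a means that they are nearly alike.

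| a | Fisher | Unstratified MH | Stratified MH | Gain over Fisher | Of which stratification |
|---|---|---|---|---|---|
| 0.3 | 46% | 49% | 57% | 11 | 8 |
| 1 | 57% | 59% | 63% | 6 | 4 |
| 3 | 64% | 66% | 67% | 3 | 1 |
| 50 | 67% | 68% | 68% | 1 | 0 |

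Each row rests on 3,000 simulated trials, so the standard error is about √(0.6 × 0.4 / 3,000) = 0.9 points per cell. A second run of the model gave ranges of 46-65%, 48-66% and 57-68% for the three tests. Together these support a gain of about 2 to 11 points, of which 0 to 9 come from stratification. Type I error was near 4% for Fisher and near 5% for the stratified test.

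**6. Sensitivity to the gradient.** With hand-set negative rates in three strata, also averaging about 30% on placebo and at odds ratio 2.5:
- Rates of 45%, 25% and 10%: Fisher 53.5%, unstratified 55.5%, stratified 61.4%.
- Rates of 55%, 15% and 3%: Fisher 32.7%, unstratified 36.2%, stratified 50.2%.

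The second gradient is steep and gives a larger gain (17.5 points, 14.0 of them from stratification). The size of the gain therefore depends on a relation that the documents do not describe.

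**The case against.** The strongest reply is that nothing is broken. Selection on a positive biopsy acts equally on both randomized arms, Fisher holds its size, and chance imbalance in core count is already covered by that error rate. The endpoint is exploratory and unpowered, and 8.2.6 already looks at change in extent. The objective compares proportions, whereas a stratified analysis leads with a conditional odds ratio. If men are nearly alike, the gain is negligible. All of this stands. It sets the priority at optional and is why Fisher should stay as a supportive analysis with the crude proportions reported. It does not explain why a baseline variable already collected should go unused, and an adjustment chosen after unblinding would be open to selection.

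A further fair point is that entry may rest on targeted cores and the later biopsy may be TRUS-guided or MR-US fusion, so several targeted cores from one lesion could inflate a count. The adjustment must therefore say which cores count. The model in step 5 covers random cores only.

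A reader might infer more: that 30% of untreated men become responders through sampling error alone. The documents do not support this. The 30% is one planning projection for both arms with no stated cause, controls receive empty vector, and the plan does not call these men responders. If 30% were instead an average over both arms, a 35% vaccine rate would imply (0.30 × 135 − 0.35 × 90) / 45 = 20% on placebo.

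**Conclusion.** The point holds as an optional precision gain, not as an error. The endpoint is the complement of the entry rule, the planned test is valid, and it leaves out a baseline variable that plausibly predicts the outcome. At odds ratio 2.5 and 90 v 45 men, adjustment is worth about 2 to 11 points of power over Fisher, with 0 to 9 from stratification and the remainder from Fisher's conservatism. This rests on the beta-binomial form, 12 cores at both biopsies, 1 to 6 positive at entry and a 30% negative rate. The link between core count and a negative repeat biopsy is assumed, not documented.

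Two stronger conclusions should not be drawn. The Fisher test is not biased. Nor do the documents show that most negative biopsies come from men with one positive core: the model puts that share at 57% to 72%, but this is model output. Since 8.2.7 and 13.5 both specify a between-arm comparison, the caution about reading one arm alone concerns reporting and is not a fault in the planned analysis.

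**What to change.** In section 13.5, pre-specify the following for 8.2.7:

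- A Cochran-Mantel-Haenszel or logistic analysis adjusted for the number of positive **random** cores on the pre-intervention biopsy, in categories 0-1, 2 and 3 or more, where 0 means positive on targeted cores only.
- The adjusted odds ratio with its confidence interval, and the proportion with no cancer by arm, overall and within each category.
- Fisher's exact test retained as supportive.
- A sentence stating that the result is read only as a between-arm comparison, because the plan's own projection is about 30% tumor-negative biopsies in each arm.

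The cost is a few sentences of SAP text. The core counts come from pathology reports already collected, and no participants, visits or procedures are added.

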13. STATISTICAL CONSIDERATIONS

13.1 Study Design/Description

This study utilizes a Phase II double-blind, randomized, placebo controlled design to assess the effect of PROSTVAC® in patients with clinically localized prostate cancer undergoing active surveillance. Each eligible participant will be randomly assigned to receive either PROSTVAC® or matched placebo. Due to potential withdrawals and the absence of tumor in the post-intervention biopsy, 25% or more participants may not provide endpoint data. All of the statistical analysis (both primary and secondary analysis) will be based on the intent-to-treat principle. Multiple imputation (MI) techniques will be applied, as necessary, for participants without endpoint data. The statistical analysis based on Rubin's rules will be performed on the imputed datasets, if MI is performed.

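### The primary test for CD8+ and CD4+ is picked from the data, and the Wilcoxon fallback drops the mean-change hypothesis under the plan's own 2:1 SD assumption and has no stated way to be pooled after imputation

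*Combined protocol and SAP*

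**What the plan says.** - **Primary test (13.4).** "A two-sided two-sample t test will be used to compare the change in" CD4+ and CD8+ between arms, with Bonferroni splitting the 5% into "a significance level of 2.5% for each". The plan does not say whether the test assumes equal variances.
- **Variance assumption (13.4).** The SD of change "for the PROSTVAC group is twice that of the placebo group". On that basis "the power will be at least 90% to detect" a Cohen's d of 0.63 or more with 63 and 31 evaluable men.
- **Data-driven sequence (end of 13.5).** For all endpoints, primary included, the data are checked for non-normality and a transformation is looked for if the check fails. As the last step, "If no suitable transformations can be found, nonparametric tests (e.g. Wilcoxon Rank Sum test and Spearman correlation coefficient) will be used". The section names no normality test, test level, candidate transformation, or effect measure to accompany a rank test.
- **Missing data (13.1, 13.4, 13.5).** Analysis is by intention to treat. Multiple imputation (MI) is used where judged necessary, and analysis by Rubin's rules "will be performed on the imputed datasets, if MI is performed". Section 13.5 extends MI to the secondary endpoints and names Fisher's exact test for the two binary biopsy endpoints. It expects at least a quarter of values to be missing.

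**The concern.** Two parts of the plan do not fit together.

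First, the trial is powered on a difference in mean change. A t test and a Wilcoxon test address the same null only if the arms differ by a pure shift or not at all. A 2:1 SD ratio rules out a pure shift. The fallback therefore swaps the hypothesis as well as the test, and the swap depends on the outcome data. A transformation also changes which mean is compared.

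Second, Rubin's rules combine an estimate and its variance from each imputed dataset. A Wilcoxon or Fisher p value is neither, and no estimator, standard error or combining rule is given for these tests.

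At stake are the meaning and the error rate of both primary comparisons. If the sequence ends in Wilcoxon, a significant result could not be read as a difference in mean change, and the analyst would have to devise the pooling after seeing the data.

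**Working it through.** **1. The plan's own figures**

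Evaluable men (13.4: 10% attrition, 70% of post-intervention biopsies with tumor): 100 × 0.9 × 0.7 = 63 and 50 × 0.9 × 0.7 = 31.5, stated as 31. Projected share without primary data: 1 − 0.9 × 0.7 = 37%.

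Power, taking the placebo SD as 1 and the PROSTVAC SD as 2:
- Pooled SD weighted by degrees of freedom: √[(62×4 + 30×1)/92] = 1.738. Difference at d = 0.63: 0.63 × 1.738 = 1.095.
- Unequal-variance (Welch) SE: √(4/63 + 1/31) = 0.309. Noncentrality: 1.095/0.309 = 3.54, with about 92 df.
- Power at two-sided 2.5%: 89.4%, which matches the stated 90% to within rounding.

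Other readings miss it. The equal-variance t test with the same pooled SD gives 76.7%. Welch with the simple average of the two variances gives 82.5%. The stated power thus implies a mean-based, unequal-variance test.

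**2. Why Wilcoxon asks a different question at SD 2:1**

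Take a right-skewed case with a closed form. Let E and E′ be independent unit exponentials, with placebo change Y = E − 1 and PROSTVAC change X = 2(E′ − 1). Both means are 0 and the SDs are 1 and 2. Then

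P(X > Y) = P(E′ > (E+1)/2) = e^(−1/2) / 1.5 = 0.607/1.5 = 0.404.

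Mean changes are equal, yet P(X>Y) is not 1/2, so Wilcoxon is right to reject its own null and wrong about the means. With right skew, these rejections point to lower ranks on PROSTVAC.

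**3. Rejection rates under equal mean change**

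Simulation, 63 v 31, nominal two-sided 2.5%, 40,000 runs. The shapes are assumptions.

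| Shape of change | SD ratio | Wilcoxon | Welch |
|---|---|---|---|
| Normal | 1:1 | 2.5% | 2.6% |
| Normal | 2:1 | 1.3% | 2.5% |
| t, 3 df | 2:1 | 1.5% | 2.2% |
| Laplace | 2:1 | 1.6% | 2.5% |
| Exponential | 2:1 | 20.6% | 2.4% |
| Log-normal, log-SD 0.75 | 2:1 | 22.5% | 2.4% |
| Log-normal, log-SD 1 | 2:1 | 45.9% | 2.2% |

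Separate runs with log-SD 0.5 to 0.8 gave Wilcoxon 8% to 27% and Welch about 2%. With equal SDs, Wilcoxon stayed at 2.2% to 2.5% in every shape tried.

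**4. With the transformation step included**

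The sequence was run as Shapiro-Wilk at 5% per arm, then Yeo-Johnson, then a re-test, with Wilcoxon if that failed (400 runs, Monte Carlo SE about 2 points). With SD 2:1 and equal means:
- log-SD 0.8: the full sequence rejected 27%, Welch 1.5%
- log-SD 0.5: the full sequence rejected 11%, Welch 2%

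When pre and post densities were log-normal (log-SD 0.8), Wilcoxon was reached in 91% to 94% of trials. Changes take both signs, so a plain log of the change is not available.

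**5. Pooling after imputation**

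Rank quantities can be pooled if a rule is written down. With 100 v 50 men, 37 and 19 of them imputed, normal data and SD 2:1, Rubin pooling of the win probability with its SE rejected 2.9%. Pooling the standardized Wilcoxon statistic rejected 1.8% (2,000 runs, Monte Carlo SE about 0.35 points). The two choices differ, and the plan names neither.

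**The case against.** The other side has good arguments.

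- **The inflation needs a particular null.** The vaccine must double the spread, leave the arithmetic mean unchanged and produce a skewed change. The 2:1 ratio is a power assumption, not a statement about the null, and the documents say nothing about skewness. If the vaccine does nothing, the arms are identical and Wilcoxon has the right size. This stands, so the 8% to 46% range is conditional.
- **A transformation comes before any rank test.** True. Under the skewed shapes tried, including the step did not remove the problem, but the plan leaves the transformation open, so another choice could behave differently.
- **MI is optional.** A reader might infer that the fallback cannot be run at all. The documents do not support that. Without MI, Wilcoxon runs as written; with MI, a rank-based estimate can be pooled once specified. What is missing is the rule.
- **Removing the pre-test does not itself buy power.** A reader might credit it with the gain that ANCOVA shows. In log-normal simulations (log-SD 0.8, log shift 0.55, pre-post correlation 0.2/0.4/0.6), Wilcoxon on raw change had 61/72/88% power and an unadjusted t test on log change 58/71/88%. The gain comes from baseline adjustment.
- **A log-scale model also changes the question.** It compares geometric means. With equal arithmetic mean change and SD 2:1, a robust log-scale ANCOVA rejected in 65% to 69% of runs. This stands, and it is why the log scale is not proposed below as the default.
- **The Fisher gap concerns endpoints the plan calls exploratory.** True; it is the lesser part of the point.

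**Conclusion.** The concern holds in limited form. The choice of primary test is data-driven and loosely specified, and under the plan's own SD ratio its last step replaces equal mean change with P(X>Y) = 1/2. Read as a test of mean change, that step can reject in roughly 8% to 46% of trials at nominal 2.5% if the change is right-skewed. It rejects in 1.3% to 1.6% if the change is symmetric, and at the nominal rate if the arms are identical. Skewness is our assumption throughout.

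For MI, the plan is under-specified, not unworkable. MI remains conditional, but intention-to-treat analysis with 37% projected missing makes it likely, and neither Wilcoxon nor Fisher then has a stated estimate, standard error or combining rule. The documents do not support a general claim that the trial's type I error is inflated.

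**What to change.** - **Primary analysis.** Stop using the normality test to select it. State one analysis for each of CD8+ and CD4+: ANCOVA of the post-intervention value on arm, pre-intervention value and the stratification factors (site, number of repeat biopsies), with heteroscedasticity-robust standard errors, at 2.5% each. It keeps the mean-change hypothesis and yields an estimate and SE that Rubin's rules can pool if MI is used.
- **Sensitivity analyses.** Keep Wilcoxon, Spearman and a log-scale analysis here, with the effect measure named. If rank results are to be reported after MI, state the pooled quantity and its variance.
- **If the log scale is preferred as primary.** Say in advance that the estimand is a ratio of geometric means and how zero counts are handled.
- **Binary endpoints.** When MI is used, pool a risk difference or log odds ratio; keep Fisher's exact test for observed cases.

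The cost is SAP wording; the covariates are already collected. In log-normal simulations, robust ANCOVA on the original scale raised power from 56–81% (Welch on change) to 70–82%. The downside is that a log-scale ANCOVA reached 80/86/94% in the same kind of scenario, and at the highest pre-post correlation even Wilcoxon on raw change (88%) did better. If densities are close to log-normal, keeping the mean-change hypothesis therefore costs some power. The sponsor should make that trade in advance.
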